## 7.5. EXAMINATION OF SUBGROUPS

Subgroup analyses are to be conducted for the primary analysis of primary efficacy variable only. It should be noted that the study was not designed to detect treatment differences with high statistical power within subgroups. Subgroup analyses are only to be performed if there are at least 10 subjects in each category of the subgroup.

The following subgroups are to be assessed for the primary efficacy variable:

- Gender:
  - o Female
  - o Male
- Age (years):
  - o  $\geq 12$  to  $\leq 17$
  - o  $\geq 18$  to  $\leq 49$
  - o  $\geq 50$  to  $\leq 65$
  - o  $> 65$
- Ethnic group
  - o Caucasian
  - o Black
  - o Asian (Indian)
  - o Asian (Oriental)
  - o American Hispanic
- Asthma status

---

Document: CP007A SAP.docx

Author: [name]

Version Number:

V 2.0

Version Date:

23 Feb 2017

Template No: CS\_TP\_BS016 – Revision 3

Reference: CS\_WI\_BS005

Effective Date: 01May2012

Copyright © 2012 Quintiles Transnational Corp. All rights reserved.

The contents of this document are confidential and proprietary to Quintiles Transnational Corp. Unauthorized use, disclosure or reproduction is strictly prohibited.

- o Present
- o Absent

All subgroup variables above are from the same source as described in [Section 6.2](#): Baseline.

## 8. OUTPUT PRESENTATIONS

[APPENDIX 1](#): Programming conventions for outputs shows conventions for presentation of data in outputs.

The templates provided within this SAP describe the presentations for this study and therefore the format and content of the summary TLFs to be provided by Quintiles Biostatistics.

---

Document: CP007A SAP.docx  
Author: [name]

Version Number: V 2.0  
Version Date: 23 Feb 2017

Template No: CS\_TP\_BS016 – Revision 3  
Effective Date: 01May2012

Reference: CS\_WI\_BS005

Copyright © 2012 Quintiles Transnational Corp. All rights reserved.

The contents of this document are confidential and proprietary to Quintiles Transnational Corp. Unauthorized use, disclosure or reproduction is strictly prohibited.

## 9. DISPOSITION AND WITHDRAWALS

All subjects who provide informed consent are to be accounted for in this study.

The number and percentage of subjects that signed informed consent to CP007A, failed any inclusion/exclusion criteria and were enrolled in the study are to be presented.

The specific inclusion/exclusion criteria not met is to be listed.

The frequency and percentage of subjects included in the FAS, mITT and SAF are to be presented.

Frequency and percentage of premature withdrawals from the study and reason for withdrawals will also be presented. Premature withdrawal from the study is defined as subjects who answered "No" to "Did the subject complete the study as planned?" on the End of Study/Withdrawal/Discontinuation Visit CRF.

## 10. PROTOCOL DEVIATIONS

Protocol deviations are to be tracked on an ongoing basis throughout the conduct of the CP007A Study. All subject deviations from the Protocol that are determined to be major are to be reported in a by subject listing.

## 11. DEMOGRAPHIC AND OTHER BASELINE CHARACTERISTICS

Demographic and other Baseline characteristics are to be presented for the ENR, FAS and mITT populations.

Continuous demographic and Baseline characteristic variables (e.g. Age) are to be summarised by treatment arm using descriptive statistics (n, mean, standard deviation (SD), median, minimum and maximum). Categorical variables (e.g. Gender) are to be summarised by frequency (n) and percentage (%). The denominator for the percentages is the total number of subjects in the population treatment arm with data available.

No statistical testing is to be performed for demographic or other Baseline characteristics.

The following demographic and other Baseline characteristics are to be reported for this study and are from the same source as described in [Section 6.2](#): Baseline:

- Age (Years)
- Age group (Years), categorised as  $\geq 12$  to  $\leq 17$ ,  $\geq 18$  to  $\leq 49$  and  $\geq 50$  to  $\leq 65$

---

Document: CP007A SAP.docx

Author: [name]

Version Number:

V 2.0

Version Date:

23 Feb 2017

Template No: CS\_TP\_BS016 – Revision 3

Reference: CS\_WI\_BS005

Effective Date: 01May2012

Copyright © 2012 Quintiles Transnational Corp. All rights reserved.

The contents of this document are confidential and proprietary to Quintiles Transnational Corp. Unauthorized use, disclosure or reproduction is strictly prohibited.

- Age group, categorised as adolescents or adults, where adolescents are defined as subjects with age  $\geq 12$  and  $< 18$  years and adults are defined as subjects  $\geq 18$  years of age
- Gender [Male/Female]
- Ethnic group [Caucasian/Black/Asian (Indian)/Asian (Oriental)/American Hispanic]
- Asthma status [Absent/Present]

## 12. MEDICATIONS

Medications are to be presented by generic name and are coded using World Health Organization-Drug Dictionary (WHO-DD) Version 01-Mar-2016.

The summaries are to be sorted by descending frequency of the total number of subjects for each generic name.

Medications are to be presented separately for medications taken outside the annual Allergy Assessment Period and medications taken during the annual Allergy Assessment Period.

### 12.1. MEDICATION USE OUTSIDE ANNUAL ALLERGY ASSESSMENT PERIOD

Medication use outside of the annual Allergy Assessment Period is to be presented for the SAF population.

Medications outside of the annual Allergy Assessment Period are defined as any medications entered on the Medicines page of the monthly diary binder.

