5.2.3 Other Medication

Subjects should record the use of all concomitant medications, both prescribed and over-the-counter, into the diary. This includes medications used on both a chronic and an as-needed basis. Hormonal contraceptives may be used by FOCBP.

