6.0 STUDY CONDUCT

6.1 Schedule of Assessments

Study assessments will occur as stated in Tables 1 and 2.

Table 1 Schedule of Assessments – Study Visits

Visit	Enrolment Visit (performed on site at or after Visit 5 of CP007)	Quarterly Visits ^e	Annual Visits ^g	End of Study / Early Termination Visit (performed on site upon study completion/subject withdrawal/ discontinuation)
Duration	1 day	1 day	1 day	1 day
Informed consent / assent ^a	X			
Inclusion / Exclusion Criteria ^b	X			
Adverse Events ^c		X	X	X
Subject collects patient diary binder	X	X	X	
Subject collects digital pen ^d	X			
Subject collects Allergy Medication Kit			X	
Subject completion of monthly assessment in subject diary		X ^f	X ^f	
Collection of digital pen (and mobile 'phone if applicable) from subject				X
^a Consent/assent may be taken at the final PAC3 visit in CP007 (Visit 4F) ^b Performed at or after Visit 5 of CP007 ^c Investigator will ask non-leading questions ^d For subjects requiring a mobile 'phone for the study, a digital pen will be sent directly to the subject along with the mobile 'phone ^e Three Quarterly Visits performed each year; up to 2 of these may be performed by telephone ^f Where possible, subjects should complete the monthly assessment during all on-site Quarterly and Annual Visits (not required for 'phone-call visits) ^g Annual Visit performed at site once per year prior to the Allergy Evaluation Period				

Table 2 Schedule of Assessments – Evaluations (to be recorded in the subject diary)

Assessments	Monthly Evaluations	Annual Evaluation
Duration	1 day	3 weeks
Subject completion of monthly assessments in subject diary	X	X
Daily Diary recording for 3 weeks: 
 • TRSS • ASS • Allergy medication use • Exposure to indoor cat 		X
Diagnosis of Asthma ^a		X
Change in geographic location ^b		X
6-Question ACQ (for Asthmatics only) ^b		X
RQLQ ^b		X
PSQI (adults only) ^b		X
WPAI:CIQ-AS ^b		X
Hospital / Physician office visits	X	
Number of lost work / school days	X	
Current Status / Change in Home Environment	X	
Exposure to Cat	X	
Global assessment of symptoms to cat exposure ^c	X	
Asthma Progression	X	
Concomitant medication	X	
Illnesses / Symptoms	X	
^a Completed at the start of annual Allergy Evaluation Period ^b Completed at the end of annual Allergy Evaluation Period ^c For subjects who no longer live in a house with an indoor cat		

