6.2.2 Monthly and annual assessments

Subjects will complete their subject diary on a monthly basis. Additionally, on an annual basis, subjects will participate in an Allergy Evaluation Period; a 3-week period where subjects will complete a number of questionnaires (to occur at the same time each year, coordinated with the Baseline Allergy Evaluation period [Visit 2A to Visit 2B] in CP007).

To support completion of data, email, SMS text messages and/or 'phone calls will be sent and/or made to subjects to remind them to complete both monthly assessments and the Allergy Evaluation Period assessments.

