6.2.3 Quarterly / Annual Visits

Subjects will have up to four visits each year; three Quarterly Visits and one Annual Visit. The visits will be conducted at approximately three-monthly intervals. The Annual Visit must take place just prior to the Allergy Evaluation Period and must be conducted on-site. At least one of the three Quarterly Visits must be conducted on-site; the remaining visits can be conducted either on-site or via telephone. There will therefore be a minimum of two on-site visits per year.

During each visit (Quarterly and Annual), sites will record any AEs/SAEs and subjects will collect (or be sent) a new diary binder with the next set of monthly assessments to complete. For on-site visits, where possible, subjects will also be instructed to complete the closest monthly assessment in the subject diary during the visit. Subjects should complete the assessment by themselves without the influence of the site staff. For telephone visits, subjects will be reminded to complete their monthly assessment at home.

During the Annual Visits, subjects will be provided with an Allergy Medication Kit, further monthly diary binders and the diary binder pertaining to the Allergy Evaluation Period. In order to ensure consistency with results obtained from CP007, the Allergy Medication Kit will contain the same therapies as provided to subjects while participating in CP007. The medications are to be used on an ‘as needed’ basis in accordance with the Allergy Medication Plan (Appendix 1).

Subjects will not be required to undergo any other specific treatment or lab tests while participating in this follow-up study. All other physician visits and treatments / procedures will be administered per the physician’s direction.

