The annual Allergy Evaluation Period for CO007A is defined as a 3-week (21 day) period, taking place at the same time of year as the 3-week Baseline Allergy Evaluation visit in CP007 (Visits 2A and 2B) and is to include:

- At the start of the 3-week Allergy Evaluation Period
  - o Diagnosis of asthma
- Daily recording for 3 weeks
  - o Rhinoconjunctivitis symptoms
  - o Asthma symptoms
  - o Allergy medication use
  - o Exposure to indoor cat
- At the end of the 3-week Allergy Evaluation Period
  - o Change in geographic location
  - o 6-Question asthma control questionnaire (ACQ) excluding lung function (for asthmatics only)
  - o RQLQ
  - o PSQI (if at least 18 years old at the time of assessment)
  - o WPAI:CIQ-AS

Subjects are to have up to four study visits each year, two of which may be conducted by telephone. At each visit, site staff will record any AEs and SAEs, and at the on-site visits subjects are to be provided with their next diary binder.

Subjects will have a final End of Study Visit, which will coincide with the end of the final annual Allergy Evaluation Period assessment.

The duration of this follow-up study is to be up to 4 years for each subject.

---

Document: CP007A SAP.docx  
Author: [name]

Version Number: V 2.0  
Version Date: 23 Feb 2017

Template No: CS\_TP\_BS016 – Revision 3  
Effective Date: 01May2012

Reference: CS\_WI\_BS005

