### 12.2. MEDICATION USE DURING THE ANNUAL ALLERGY ASSESSMENT PERIOD

Medication use during the annual Allergy Assessment Period is to be presented for the FAS.

Allergy medications during the annual Allergy Assessment Period are defined as any medications entered on the “Allergy Medicines that You Have Taken in the Past 21 Days” page of the annual Allergy Assessment Period diary binder.

---

Document: CP007A SAP.docx

Author: [name]

Version Number:

V 2.0

Version Date:

23 Feb 2017

Template No: CS\_TP\_BS016 – Revision 3

Reference: CS\_WI\_BS005

Effective Date: 01May2012

Copyright © 2012 Quintiles Transnational Corp. All rights reserved.

The contents of this document are confidential and proprietary to Quintiles Transnational Corp. Unauthorized use, disclosure or reproduction is strictly prohibited.

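### SAP 12.1 decides by diary page, not by date, which medicines count as used outside the annual period, so a medicine taken only within the 21 days can be reported as outside use

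*SAP*

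**What the plan says.** SAP Section 12 sets the aim: "Medications are to be presented separately for medications taken outside the annual Allergy Assessment Period and medications taken during the annual Allergy Assessment Period". The two subsections then assign medicines by where they were written down.

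- Section 12.1, shown for the safety population: "Medications outside of the annual Allergy Assessment Period are defined as any medications entered on the Medicines page of the monthly diary binder".
- Section 12.2, shown for the FAS: "Allergy medications during the annual Allergy Assessment Period are defined as any medications entered on the" page of the annual binder that lists allergy medicines from the last 21 days.

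Neither subsection tests a date, and neither says what happens to a medicine that appears on both pages.

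On timing, SAP 3.1 says the annual period "is defined as a 3-week (21 day) period". Protocol 6.2.2 places it on top of the monthly diary: "Additionally, on an annual basis, subjects will participate in an Allergy Evaluation Period; a 3-week period where subjects will complete a number of questionnaires". Protocol 6.2.3 has everything issued together at the Annual Visit, where "subjects will be provided with an Allergy Medication Kit, further monthly diary binders and the diary binder pertaining to the Allergy Evaluation Period". In Protocol 6.1, Table 2, the row "Subject completion of monthly assessments in subject diary" is marked under both the monthly and the annual column. The separate row for concomitant medication is marked under the monthly column only. Protocol 5.2.3 adds: "Subjects should record the use of all concomitant medications, both prescribed and over-the-counter, into the diary", and this includes medicines taken as needed.

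**The concern.** The tables are titled by time of use but filled by source page. The two agree only if no monthly page ever carries a medicine taken solely within the annual period, and nothing in either document ensures that.

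The outside table is the one a reader would use to see what subjects took in ordinary life, away from the three weeks in which the sponsor supplies a kit. Protocol 3.2.2 lists concomitant medication for rhinoconjunctivitis or related conditions as a secondary endpoint, and Protocol 7.4.2.2.3 promises an evaluation of it. SAP 13.2 contains no analysis of that endpoint, so the Section 12 summaries are all that the SAP produces for it. If in-period use enters the outside table, the title misdescribes part of the content, and kit use already scored in the RMS may appear a second time under another name.

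**Working it through.** The plan states no figure on this point, so there is none to reproduce. The check has three parts.

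**1. Does the monthly diary stop for the annual period?** It does not. Table 2 marks the monthly assessments under the annual evaluation too, Protocol 6.2.2 makes the annual period additional, and SAP Appendix 1 presents Months 01 to 12 with none left out.

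**2. Must a monthly page overlap the 21 days?** Assume contiguous pages of 30 days each. Other monthly items look back over the past month (SAP 13.2.1.5, 13.3.1.5 and 13.3.1.6). Place the 21-day window at each of the 30 possible start days:

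- It fits within one page when it starts on any of the first 30 − 21 + 1 = 10 days.
- It straddles two pages for the other 30 − 10 = 20 start days.
- When 21 days are split over two pages, the larger part is at least 11 days.

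So one or two monthly pages a year overlap the period, and one of them always covers at least 11 in-period days.

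**3. What could the page rule do to the outside table?** Let q be the true share using a medicine outside the period, k the share using it from the kit within the period, and e the share of kit users who also write it on the monthly page, taken as independent. The table then shows

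q + (1 − q) × k × e.

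None of these inputs is in the documents; all values below are assumptions. With q = 0.20 and k = 0.60:

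| e | Calculation | Shown as outside |
|---|---|---|
| 0.10 | 0.20 + 0.80 × 0.60 × 0.10 | 24.8% |
| 0.50 | 0.20 + 0.80 × 0.60 × 0.50 | 44.0% |
| 1.00 | 0.20 + 0.80 × 0.60 × 1.00 | 68.0% |

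Within an arm the error can only be upward. At e = 0 there is none from kit medicines.

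For the difference between arms, take true outside use of 20% on active and 30% on placebo (10 points), with e = 0.70:

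- Kit use 60% in both arms: 1 − 0.80 × (1 − 0.42) = 53.6% and 1 − 0.70 × (1 − 0.42) = 59.4%. The gap narrows to 5.8 points.
- Kit use 50% on active and 60% on placebo: 1 − 0.80 × (1 − 0.35) = 48.0% and 59.4%. The gap widens to 11.4 points.

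The direction of the effect on a contrast therefore depends on how kit use differs between arms.

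**The case against.** The strongest reply is that kit medicines may never reach the monthly page. Protocol 5.2.3 is headed Other Medication, while the kit has its own section, 5.2.1. Protocol 5.2.3 speaks of the diary without naming the monthly Medicines page, and the annual binder is a diary binder too. Kit use has its own recording route: daily entries in the annual period (Protocol 6.3.2) and the annual page used by SAP 12.2. Table 2 marks concomitant medication under the monthly column only. The Medicines page, its instructions and any date fields are not in the documents.

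All of this stands. A reader might infer that subjects are told to enter kit medicines on the monthly page, and that those medicines are therefore counted as outside use. The documents do not support that: the entry is possible, but it is neither instructed nor shown to happen. The monthly-only mark in Table 2 leaves the matter unclear. It does not stop a monthly page from covering in-period days.

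The reply does not remove the mismatch. Section 12.2 takes allergy medicines only, so a non-allergy medicine taken only within the 21 days has nowhere to go but the monthly page, and there Section 12.1 labels it outside use. That part does not depend on the kit.

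It is also fair to say that the summaries are descriptive, and that a medicine listed in both is not double counting in itself, because the tables are separate.

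**Conclusion.** The definition in SAP 12.1 is wrong as written: it does not deliver the split by time of use that Section 12 announces. The mislabelling of any medicine taken only within the 21 days and entered on a monthly page follows from the text, provided that monthly pages run without gaps. Its frequency cannot be established, and the percentages in the working illustrate assumed values only.

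Two stronger readings should be set aside. A reader might conclude that differences between arms are diluted. That holds when kit use is equal across arms but can reverse when it is not. A reader might also take the overlap as a fixed 21 days of a single page. With 30-day pages, that is so for only 10 of 30 start days.

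The consequence is limited to the descriptive Section 12 summaries. The daily RMS and the Combined Score are built from the daily recording in the annual period and do not change. The point still deserves correction because those summaries are the only SAP output for a listed secondary endpoint.

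**What to change.** Where the monthly page records dates:

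- Count an entry as outside only if its dates include at least one day outside that subject's Day 1 to Day 21 for the year.
- Show entries that lie wholly within Day 1 to Day 21, non-allergy medicines included, in the during summary, so that they do not drop out of both tables.
- Count a medicine entered on both the monthly and the annual page once in the during summary.
- State which population applies to the moved entries, because 12.1 uses the safety population and 12.2 the FAS.

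Where the page has no dates, title the tables by source (monthly diary, annual diary) and show separately the one or two monthly pages a year that overlap the period.

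The cost is revised SAP wording and a small amount of programming. Without dates, one or two months a year are shown apart from the rest, and some genuine outside use goes with them. No new data are needed, and neither the significance level nor the power is affected.

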### 12.2. MEDICATION USE DURING THE ANNUAL ALLERGY ASSESSMENT PERIOD

Medication use during the annual Allergy Assessment Period is to be presented for the FAS.

Allergy medications during the annual Allergy Assessment Period are defined as any medications entered on the “Allergy Medicines that You Have Taken in the Past 21 Days” page of the annual Allergy Assessment Period diary binder.

---

Document: CP007A SAP.docx

Author: [name]

Version Number:

V 2.0

Version Date:

23 Feb 2017

Template No: CS\_TP\_BS016 – Revision 3

Reference: CS\_WI\_BS005

Effective Date: 01May2012

Copyright © 2012 Quintiles Transnational Corp. All rights reserved.

The contents of this document are confidential and proprietary to Quintiles Transnational Corp. Unauthorized use, disclosure or reproduction is strictly prohibited.

## 13. EFFICACY OUTCOMES

### 13.1. PRIMARY EFFICACY

#### 13.1.1. PRIMARY EFFICACY VARIABLE & DERIVATION

The primary efficacy variable is the daily Combined Score (CS) of the 3-week annual Allergy Assessment Period completed after Year 1 to Year 4 in the subject's annual assessment diary binder.

The daily Total Rhinoconjunctivitis Symptom Score (TRSS) and the daily Rescue Medication Score (RMS) are to be combined and a daily CS is to be calculated for each subject as follows:

- $CS = (TRSS / 8) + RMS$

For the primary analysis, for each subject the mean of the daily non-missing CS during the annual Allergy Assessment Period is to be calculated as follows:

- $Sum(\text{Day 1 CS to Day 21 CS}) / \text{Number of non-missing days}$

The mean CS is to be calculated over the 21 days of the annual Allergy Assessment Period for each subject based on the data available for the non-missing days if a subject does not complete the whole annual assessment period.

The TRSS is the sum of eight individual TRSS symptom scores, namely runny nose, sneezing, blocked nose, itchy nose, itchy eyes, watery eyes, red eyes and sore eyes. All symptoms are reflective over the previous 24 hours.

For each symptom, the subject will rate (on a daily basis for the duration of the Allergy Assessment Period) the severity as follows:

0 = absent

1 = mild, barely noticeable

2 = moderate, annoying/troublesome

3 = severe, very annoying/very troublesome

The TRSS will have a range of 0 to 24. The TRSS on each day is to be calculated as follows:

TRSS = Runny Nose + Sneezing + Blocked Nose + Itchy Nose + Itchy Eyes + Watery Eyes + Red Eyes + Sore Eyes.

---

Document: CP007A SAP.docx

Author: [name]

Version Number:

V 2.0

Version Date:

23 Feb 2017

Template No: CS\_TP\_BS016 – Revision 3

Reference: CS\_WI\_BS005

Effective Date: 01May2012

Copyright © 2012 Quintiles Transnational Corp. All rights reserved.

The contents of this document are confidential and proprietary to Quintiles Transnational Corp. Unauthorized use, disclosure or reproduction is strictly prohibited.

Allergy medications are to be provided to subjects to be used according to a pre-specified Allergy Medication Plan (Appendix 1 in Protocol). The use of allergy medications are to be scored based on Didier (Didier *et al*, 2009) as follows:

- RMS = 0; no allergy medication used per day
- RMS = 0.5; at least one dose of antihistamine eye drops used per day
- RMS = 1; at least one dose of oral antihistamine used per day
- RMS = 2; at least one dose of intranasal corticosteroid used per day
- RMS = 3; at least one dose of systemic corticosteroid used per day

The RMS score is not additive, the maximum value per day is used and therefore the maximum RMS per day is 3.

If any of the eight individual TRSS, namely sneezing, runny nose, blocked nose, itchy nose, itchy eyes, watery eyes, red eyes or sore eyes for a given day is missing, the TRSS for that day is to be considered missing. If either the TRSS or the RMS is missing for a particular day then the CS will also be considered missing.

